#### 9.1 PRIMARY EFFICACY ENDPOINT

The primary efficacy assessment is masseter muscle prominence assessed by the investigator using the MMPS (1 = minimal, 2 = mild, 3 = moderate, 4 = marked, 5 = very marked).

The primary efficacy endpoint is the achievement of  $\geq$  2-grade improvement from baseline at Day 90 using the MMPS.

The following set of hypotheses will be used to compare the BOTOX 72 U group with placebo:

- Null hypothesis: BOTOX and placebo are equally effective in reducing MMP as measured by the proportion of participants achieving ≥ 2-grade improvement from baseline at Day 90 using the MMPS.
- Alternative hypothesis: BOTOX and placebo are not equally effective in reducing MMP as measured by the proportion of participants achieving ≥ 2-grade improvement from baseline at Day 90 using the MMPS.

The proportion of participants who achieve  $\geq$  2-grade improvement from baseline, per investigator assessments of MMP using the MMPS, will be analyzed using Cochran-Mantel-Haenszel (CMH) model stratified by baseline MMPS Grade (4 or 5) at each visit. A 2-sided p-value  $\leq$  0.05 will be claimed as statistically significant. The Breslow-Day homogeneity of the odds-ratio test will be performed to test the interaction of treatment by baseline MMPS Grade. A

two-sided p-value  $\leq$  0.1 will be claimed as statistically significant. Responder rate 2-sided 95% CIs within each treatment group will be based on normal approximation to the binomial.

Sensitivity analyses will be performed for the primary efficacy variable based on observed data.

The attributes of the estimands corresponding to the primary efficacy endpoint are summarized in Table 2.

Table 2. Summary of the Estimand Attributes of the Primary Efficacy Endpoint

	Attributes of the Estimand							
Estimand Label	Treatment	Endpoint	Population	Handling of Intercurrent Events	Statistical Summary			
Hypothetical estimand for primary endpoint	BOTOX 72 U vs placebo	Achievement of ≥ 2-grade improvement from baseline based on MMPS at Day 90	mITT (all randomized participants with at least one postbaseline MMPS assessment)	Participants who discontinue prior to Day 90 assessments or who do not have Day 90 MMPS assessments will be included in the analysis as a hypothetical scenario in which they had not missed the MMPS assessments	Difference in response proportions between treatments after MI using CMH test stratified by baseline MMPS			

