Period 1 (Days 1 through 180) will be a double-blind, randomized, placebo-controlled, single-treatment design, which will assess the safety and efficacy of BOTOX treatment of MMP. On Day 1, participants will be randomized in a 3:1 ratio to receive BOTOX 72 U or placebo. Randomization will be stratified at each investigator site by the participant's baseline MMPS Grade (4 or 5). On Day 180, final Period 1 assessments will be collected, after which all participants will continue into Period 2, the open-label treatment portion of the study.

Period 2 (Days 180 through 540) will be open-label. All BOTOX and placebo-treated participants from Period 1 are eligible to receive up to 2 open-label treatments of BOTOX 72 U in Period 2 if they meet protocol-specified retreatment criteria on or after the Day 180 visit. If the participant does not meet the retreatment criteria at the Day 180 visit, he or she will be reassessed at the next visit. For Treatment 2, participants who qualify can be retreated from the Day 180 visit through the Day 420 visit. For Treatment 3, the earliest visit that participants may qualify and receive the third treatment is the Day 270 visit (3 months after the earliest visit for Treatment 2 [Day 180 visit]). The last visit that participants may qualify and receive treatment

(either Treatment 2 or Treatment 3) is

Retreatment Criteria:

- Participant has presence of MMP of at least marked (Grade 4) on each side, as assessed by the investigator using the MMPS, AND
- Females of childbearing potential must have a negative pregnancy test prior to treatment,
 AND
- If it is the third treatment, at least 3 months have lapsed since the previous study treatment

If a participant qualifies for retreatment in Period 2 and declines it, retreatment will not be administered at that visit and the participant's reason for declining retreatment will be captured on the eCRF. If the participant still meets retreatment criteria at the next visit (up to Day 420), he or she may receive retreatment at that time.

Number of Participants:

Approximately 360 participants will be enrolled in order to have 306 participants complete the study based on an anticipated dropout rate of 15%.

- Approximately 235 participants will be enrolled from China (mainland).
- Approximately 75 participants will be enrolled from Canada.
- Approximately 50 participants will be enrolled from Taiwan.

Number of Sites:

Approximately 30 sites in China (mainland), Canada, and Taiwan

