9.2. Sample Size Determination

approximately 360 participants (270 BOTOX and 90 placebo) will provide > 90% power

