## 9.0 EFFICACY ANALYSES

The efficacy analyses will be based on the mITT population. Baseline for efficacy is defined as the last approved (imaging data) non-missing efficacy assessment before the first dose of study treatment. Pairwise comparisons will be conducted between BOTOX 72 U group and the placebo group. All statistical tests will be 2-sided hypothesis tests performed at 5% level of significance for main effects, with Type I error controlled as described further in Section 14.0.

For the primary and secondary efficacy variables, subjects with missing values at a given visit will be imputed using multiple imputation (MI) up to Day 180 in Period 1. The other efficacy variables will not be imputed.

For subjects who continue in Period 2, efficacy visits beyond Day 180 but prior to retreatment (if any) will be displayed by assigned treatment group in double-blind treatment cycle 1.

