## 9.2 SECONDARY EFFICACY ENDPOINTS

The secondary efficacy endpoints are:

- Achievement of MMPS Grade ≤ 3 at Day 90, according to investigator
- Achievement of MMPS-P Grade ≤ 3 at Day 90, according to participant
- Achievement of ≥ 2-grade improvement from baseline at Day 90 using the MMPS-P
- Achievement of PSAC Grade ≥ 1 (at least minimally improved from baseline) at Day 90
- Change from baseline in lower facial width (mm) at Day 90

Duration of effect for BOTOX-treated MMPS responders

The proportion of participants who achieve MMPS Grade  $\leq$  3, the proportion of participants who achieve MMPS-P Grade  $\leq$  3, the proportion of participants who achieve  $\geq$  2-grade improvement from baseline using the MMPS-P, and the proportion of participants who achieve PSAC Grade  $\geq$  1 will be analyzed in the same manner as that used to analyze the primary endpoint. Missing MMPS, MMPS-P, and PSAC values in Period 1 will be imputed using the same MI method as for primary endpoint.

Table 3. Summary of the Estimand Attributes of the Secondary Efficacy Endpoints

	Attributes of the Estimand								
Estimand Label	Treat- ment	Endpoint	Population	Handling of Intercurrent Events	Statistical Summary				
Hypothetical estimand for binary secondary endpoints	BOTOX 72 U vs placebo	Achievement of the following at Day 90:  • MMPS Grade ≤ 3  • MMPS-P Grade ≤ 3  • MMPS-P ≥ 2-grade improvement from baseline  • PSAC Grade ≥ 1	mITT (all randomized participants with at least one postbaseline MMPS assessment)	Participants who discontinue prior to Day 90 assessments or who do not have specified Day 90 secondary efficacy assessments will be included in the analysis as a hypothetical scenario in which they had not missed the assessments	Difference in response proportions between treatments after MI using CMH test stratified by baseline MMPS				
Hypothetical estimand for continuous secondary endpoints	BOTOX 72 U vs placebo	Change from baseline in lower facial width (mm) at Day 90	mITT (all randomized participants with at least one postbaseline MMPS assessment)	Participants who discontinue prior to Day 90 assessments or who do not have Day 90 lower facial width will be included in the analysis as a hypothetical scenario in which they had not missed the lower facial width assessments	Difference between treatments in LS Mean and SE after MI using ANCOVA				

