## 15.0 DETERMINATION OF SAMPLE SIZE

approximately 360 participants (270 BOTOX and 90 placebo) will provide

> 90% power

[figure not shown]

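### Within-arm responder-rate 95% CIs use the normal approximation, which can fail in the roughly 90-participant placebo arm if few placebo participants respond (descriptive precision only)

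*SAP*

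**What the plan says.** SAP Section 9.1 fixes the interval for each arm's responder rate: "Responder rate 2-sided 95% CIs within each treatment group will be based on normal approximation to the binomial". The rule is unconditional in the visible text, with no exact or score interval for zero or few responders.

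The rule applies to more than one table:

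- Section 9.1 analyses the responder proportion at every visit, not only Day 90.
- In the main analysis, SAP Section 9.0 says that "subjects with missing values at a given visit will be imputed using multiple imputation (MI) up to Day 180 in Period 1". For the supporting analysis, Section 9.1 says: "Sensitivity analyses will be performed for the primary efficacy variable based on observed data".
- SAP Section 9.2 says that the four binary secondary endpoints "will be analyzed in the same manner as that used to analyze the primary endpoint", which plausibly carries the interval rule to them.

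On arm size, Protocol Section 9.2 says "approximately 360 participants (270 BOTOX and 90 placebo) will provide > 90% power"; SAP Section 15.0 gives the same 270 and 90. The assumed responder rates are not visible in either document.

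**The concern.** The normal-approximation (Wald) interval estimates its width from the observed proportion alone. When few or no events are seen, the estimated width collapses and the interval is too short, mainly on the upper side.

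The placebo arm is where this could happen. Entry requires MMPS Grade 4 or 5 (Protocol Section 5.1), so a placebo responder must move from 4 to 2 or lower, or from 5 to 3 or lower. With 3:1 allocation the placebo arm is also the small one. Among the secondary endpoints, the 2-grade MMPS-P responder rate sets the same hurdle, because entry also requires MMPS-P Grade 4 or 5. The other three binary secondary endpoints need a smaller change and are less exposed.

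At stake is the stated precision of the placebo response on the primary endpoint. If placebo responders are few, the upper limit will be too low, and the report may show a 0% to 0% interval or a negative proportion.

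**Working it through.** **Inputs.** Placebo n = 90 (Protocol Section 9.2, SAP Section 15.0). Allocation 3:1, 306 completers and 15% dropout (Protocol Section 1.1). Interval method and 95% level from SAP Section 9.1. True placebo rate: not visible, so 1% to 20% is assumed.

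**The plan's own figures.** 306 / (1 − 0.15) = 360, and 360 split 3:1 is 270 and 90. Both reproduce. The stated power above 90% cannot be reproduced without the assumed rates, and nothing below depends on it. The documents state no interval width or coverage.

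**Intervals at low counts, n = 90.** Wald: p̂ ± 1.96·√[p̂(1 − p̂)/n]. The lower limit is negative when 0 < p̂ < z²/(n + z²) = 3.84/93.84 = 4.1%, that is, for 1 to 3 responders.

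| Responders | Wald 95% CI (%) | Wilson 95% CI (%) |
|---|---|---|
| 0 | 0 to 0 | 0 to 4.1 |
| 1 | −1.05 to 3.28 | 0.2 to 6.0 |
| 2 | −0.82 to 5.27 | 0.6 to 7.7 |
| 3 | −0.38 to 7.04 | 1.1 to 9.4 |
| 4 | 0.19 to 8.70 | 1.7 to 10.9 |

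**How often, n = 90.** P(zero width) = (1 − p)^90, for example 0.99^90 = 0.405. Coverage is the sum of binomial probabilities over the counts whose interval contains p (exact enumeration).

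| True rate | Zero width | Negative lower limit | Wald coverage | Wilson coverage |
|---|---|---|---|---|
| 1% | 40% | 58% | 59.5% | 93.8% |
| 2% | 16% | 73% | 83.5% | 96.5% |
| 4% | 2.5% | 49% | 87.6% | 97.2% |
| 5% | 1.0% | 33% | 93.8% | 95.4% |
| 10% | 0.01% | 1.7% | 94.6% | 95.0% |
| 15% | 0% | 0.03% | 92.4% | 96.3% |
| 20% | 0% | 0% | 94.7% | 95.3% |

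**Direction of the misses.** Intervals lying wholly below the true rate versus wholly above it: 40% v 0.03% at a 1% rate, 16% v 0.2% at 2%, 5.7% v 0.5% at 5%. At 1% and 2% every low miss comes from the zero-responder case. At 4% and 5% a single responder also misses, since its upper limit is 3.28%. Negative limits lose no coverage if cut at 0, so they are a display defect.

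**Observed-data table.** If the full 15% study dropout had already occurred by Day 90 (a worst case), 90 × 0.85 = 76.5, taken as 77. At 1% / 2% / 5% / 10%, zero width has probability 46% / 21% / 1.9% / 0.03% and Wald coverage is 53.9% / 78.8% / 89.8% / 94.8%.

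**After multiple imputation.** Zero width then needs no responder in any imputed data set, so it is less frequent. This was simulated under stated assumptions: n = 90, 10% of Day 90 values missing at random, beta-binomial imputation of responder status with a Jeffreys prior, 20 imputations, Rubin's rules with t limits, 20,000 replicates.

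| True rate | Zero width | Normal-approximation coverage |
|---|---|---|
| 1% | 16% | 69% |
| 2% | 7% | 80% |
| 5% | 0.6% | 91% |
| 10% | 0% | 92% |
| 20% | 0% | 94% |

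An MI-adapted Wilson interval held 95–96% throughout. With 5% and 15% missing, zero width was 27% and 9% at a 1% rate, and 11% and 4% at 2%.

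**BOTOX arm.** At n = 270 and assumed rates of 20% to 50%, Wald coverage is 94.1–95.3%, so there is no problem in that arm.

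**The case against.** The strongest reply is that everything depends on a number that is not visible. The sponsor has Phase 2 data on 2-grade MMPS response and may have chosen the interval knowing the placebo rate. If that rate is 10% or more, the defect all but disappears. This is fair, and it is why the point is conditional. Not knowing the rate is also a reason to choose an interval that works across the range, before unblinding rather than after seeing a zero count.

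Second, nothing inferential depends on these intervals. The SAP's estimand table summarises the between-arm difference using the stratified CMH test, and the within-arm interval enters no visible decision rule. That stands and limits the point to minor.

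Third, the imputation and pooling details are not visible, and a sparse-count rule could sit in withheld text. The plan also imputes missing MMPS, MMPS-P and PSAC values, whereas the simulation imputed responder status, so the post-imputation figures are only illustrative. That stands too. The observed-data calculation needs no imputation model, and the visible interval rule carries no exception.

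Fourth, Wilson is not perfect. At n = 90 its coverage dips to 89.8% at a 0.6% rate, but the Wald figure there is 41.8%. Clopper-Pearson also removes both defects and is more conservative (97.6–99.0% coverage for rates of 0.5% to 5%).

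**Conclusion.** The concern holds, as a minor point about descriptive precision. If the true placebo rate is about 2% or below, the prescribed interval falls far short of 95% coverage (59.5% at 1%, 83.5% at 2%, n = 90), and its errors put the upper limit too low. Around 3% to 5%, n = 90 coverage is uneven (93.0%, 87.6% and 93.8% at 3%, 4% and 5%); at 5% the main symptom is a negative lower limit, about one time in three. From 10% to 20% coverage is 92.4–94.7% and the problem nearly vanishes.

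The n = 90 figures assume no missing Day 90 values. The n = 77 figures assume all dropout occurs by Day 90. The post-imputation figures rest on an assumed imputation model and pooling rule. The CMH test, familywise error control and sample size are not affected.

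**What to change.** In SAP Section 9.1, replace the normal approximation for within-arm responder rates with Wilson score intervals: ordinary Wilson for the observed-data tables, and an MI-adapted Wilson (or logit-scale pooling) for the imputed data. State that the same rule applies to the binary secondary endpoints in Section 9.2. Make the change before unblinding.

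The cost is one SAP sentence, a procedure option and a short pooling step. Intervals become asymmetric and wider where counts are low. At n = 90, with limits cut at 0, mean width goes from 4.5 to 6.7 percentage points at a 2% rate, 8.5 to 9.4 at 5%, and 12.2 to 12.4 at 10%. No change to design, testing or sample size is needed.

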## 9.2 SECONDARY EFFICACY ENDPOINTS

The secondary efficacy endpoints are:

- Achievement of MMPS Grade ≤ 3 at Day 90, according to investigator
- Achievement of MMPS-P Grade ≤ 3 at Day 90, according to participant
- Achievement of ≥ 2-grade improvement from baseline at Day 90 using the MMPS-P
- Achievement of PSAC Grade ≥ 1 (at least minimally improved from baseline) at Day 90
- Change from baseline in lower facial width (mm) at Day 90

Duration of effect for BOTOX-treated MMPS responders

The proportion of participants who achieve MMPS Grade  $\leq$  3, the proportion of participants who achieve MMPS-P Grade  $\leq$  3, the proportion of participants who achieve  $\geq$  2-grade improvement from baseline using the MMPS-P, and the proportion of participants who achieve PSAC Grade  $\geq$  1 will be analyzed in the same manner as that used to analyze the primary endpoint. Missing MMPS, MMPS-P, and PSAC values in Period 1 will be imputed using the same MI method as for primary endpoint.

Table 3. Summary of the Estimand Attributes of the Secondary Efficacy Endpoints

	Attributes of the Estimand								
Estimand Label	Treat- ment	Endpoint	Population	Handling of Intercurrent Events	Statistical Summary				
Hypothetical estimand for binary secondary endpoints	BOTOX 72 U vs placebo	Achievement of the following at Day 90:  • MMPS Grade ≤ 3  • MMPS-P Grade ≤ 3  • MMPS-P ≥ 2-grade improvement from baseline  • PSAC Grade ≥ 1	mITT (all randomized participants with at least one postbaseline MMPS assessment)	Participants who discontinue prior to Day 90 assessments or who do not have specified Day 90 secondary efficacy assessments will be included in the analysis as a hypothetical scenario in which they had not missed the assessments	Difference in response proportions between treatments after MI using CMH test stratified by baseline MMPS				
Hypothetical estimand for continuous secondary endpoints	BOTOX 72 U vs placebo	Change from baseline in lower facial width (mm) at Day 90	mITT (all randomized participants with at least one postbaseline MMPS assessment)	Participants who discontinue prior to Day 90 assessments or who do not have Day 90 lower facial width will be included in the analysis as a hypothetical scenario in which they had not missed the lower facial width assessments	Difference between treatments in LS Mean and SE after MI using ANCOVA				

## 9.3 ADDITIONAL EFFICACY ENDPOINTS

## 10.0 SAFETY ANALYSES

The safety analysis will be performed using the Safety Population. The safety parameters will include adverse events (AEs) and vital signs. For each safety parameter of vital signs, the last non-missing safety assessment before the first dose of study treatment will be used as the baseline for all analyses of that safety parameter. Continuous variables will be summarized by number of participants and mean, SD, median, minimum, and maximum values. Categorical variables will be summarized by number and percentage of participants.

For subjects who continue in Period 2, safety data beyond Day 180 but prior to retreatment (if any) will be ascribed to the double-blind treatment received in treatment cycle 1.

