Danied 2 (Davis 190 through 540/Study Evit)

Period 2 (Days 180 through 540/Study Exit)

Day 180 is considered both the end of Period 1 and the beginning of Period 2. After Period 1 assessments are collected, the participant will enter Period 2 and will be assessed for retreatment. If the participant does not meet the retreatment criteria at Day 180, he or she will be reassessed at the next visit. All BOTOX and placebo-treated participants from Period 1 are eligible to receive up to 2 open-label treatments of BOTOX 72 U in Period 2 *if* they meet the following retreatment criteria (also see Section 6.6) on or after the Day 180 visit.

- Participant has bilateral marked (Grade 4) or very marked (Grade 5) MMP, as assessed by the investigator using the MMPS, AND
- Females of childbearing potential must have a negative pregnancy test prior to treatment,
 AND
- If it is the third treatment, at least 3 months have lapsed since the previous study treatment (no retreatment earlier than 84 days)

During Period 2, participants will attend all follow-up visits (Days 210, 240, 270, 300, 330, 360, 390, 420, 450, 480, 510, and 540). For Treatment 2, participants who qualify can be retreated from the Day 180 visit through the Day 420 visit. For Treatment 3, the earliest visit that participants may qualify and receive the third treatment is Day 270 (3 months after the earliest visit for Treatment 2 [Day 180]). The last day that a participant can receive either Treatment 2 or 3 is Day 420; this ensures a 120-day safety and efficacy follow-up period by Day 540/study exit. A participant who meets retreatment criteria may decline retreatment if they choose, and their reason will be captured on the eCRF. If the participant still meets retreatment criteria at the next visit (up to Day 420), he or she may receive retreatment at that time.

In Period 2, participants will receive up to 2 additional treatments. Based on individual variability in time to meet retreatment criteria noted in the Phase 2 Study 191622-130, retreatment timepoints are not expected to be synchronized among the participants in the study.

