6.6.1. Retreatment Criteria

All participants entered into the study will be treated at Day 1. A participant will receive 1 additional treatment if she/he meets retreatment criteria, as determined by the investigator. To be eligible for retreatment at the Day 180, 210, 240, 270, 300, 330, 360, 390, or 420 visits, the participant must meet all the following criteria:

- Participant has presence of MMP of at least marked (Grade 4) on each side, as measured by the investigator using the MMPS, AND
- Females of childbearing potential must have a negative pregnancy test prior to treatment,
 AND

•	

A second treatment is only allowed on or between the Day 180 and Day 420 visits.

Retreatments must

BOTOX

occur during normally scheduled visit windows and are prepared and administered as described in Section 6.2 for BOTOX.

Treatment	Study Visit	Description
Treatment 1	Day 1 (Visit 2)	Double blind, randomized
Treatment 2 (Retreatment 1)	Days 180 to 420 (Visit 8 to 16)	Open-label; participant must qualify for retreatment
Treatment 3 (Retreatment 2)	Days 270 to 420 (Visits 11 to 16)	Open-label; participant must qualify for retreatment; must be 84 days from the previous treatment

If a participant qualifies for retreatment in Period 2 and declines it, retreatment will not be administered at that visit and the participant's reason for declining retreatment will be captured on the eCRF. If the participant still meets retreatment criteria at the next visit (up to Day 420), he or she may receive retreatment at that time.

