## 4.0 INTRODUCTION

This statistical analysis plan (SAP) provides a more technical and detailed elaboration of the statistical analyses of the efficacy and safety data as outlined and/or specified in the final protocol of Study 1789-301-008 (version dated 17 Dec 2018). Specifications of tables, figures, and data listings are contained in a separate document.

This is an 18-month, multicenter study consisting of 2 periods, a double-blind placebo-controlled single-treatment period and an open-label period in which a maximum of 2 further study treatments can be received. Up to 20 scheduled visits are planned: screening (Day -14 to Day -1), baseline (Day 1), follow-up monthly thereafter (Days 30, 60, 90, 120, 150, 180, 210, 240, 270, 300, 330, 360, 390, 420, 450, 480, 510), and study exit (Day 540).

Period 1 (Days 1 through 180) will be a double-blind, randomized, placebo-controlled, single-treatment design, which will assess the safety and efficacy of botulinum toxin type A purified neurotoxin (BOTOX) treatment of masseter muscle prominence (MMP). On Day 1, participants will be randomized in a 3:1 ratio to receive BOTOX 72 unit (U) or placebo. Randomization will be stratified at each investigator site by the participant's baseline Masseter Muscle Prominence Scale (MMPS) Grade (4 or 5). On Day 180, final Period 1 assessments will be collected, after which all participants will continue into Period 2, the open-label treatment portion of the study.

Period 2 (Days 180 through 540) will be open-label. All BOTOX and placebo-treated participants from Period 1 are eligible to receive up to 2 open-label treatments of BOTOX 72 U in Period 2 if they meet protocol-specified retreatment criteria on or after the Day 180 visit. If the participant does not meet the retreatment criteria at the Day 180 visit, he or she will be reassessed at the next visit. For Treatment 2, participants who qualify can be retreated from the Day 180 visit through the Day 420 visit.

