#### 10.1 EXTENT OF EXPOSURE

The number of treatments received will be summarized by treatment group for the Safety Population.

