#### 10.2 ADVERSE EVENTS

Adverse events will be coded by system organ class and preferred term using the *Medical Dictionary for Regulatory Activities*, version 25.1 or newer.

An AE will be considered as a treatment-emergent adverse event (TEAE) if the AE began or worsened (increased in severity or became serious) on or after the date of the first dose of double-blind study treatment.

A TEAE for treatment cycle 1 is an adverse event with onset after the initiation of study treatment or became serious after the initiation of study treatment for cycle 1.

In each of the analysis periods (treatment cycle 1 in the double-blind period, open-label period, BOTOX cycle, or BOTOX overall), a specific TEAE will only count once per participant, associated with its worst severity during the time period of interest. Unless stated otherwise, the methods of analyses described in this section will be applied to each of the study period.

TEAEs will be summarized for each treatment group by treatment cycle 1 in the double-blind period, open-label period, by BOTOX cycle, and BOTOX exposure overall. Participants will be counted according to the treatment received at baseline (Placebo or BOTOX 72 U) for treatment cycle 1. For open-label period and Any BOTOX exposure tables, participants will be summarized according to the treatment received at cycle 1 baseline and treatment received during open-label (Placebo/BOTOX 72 U or BOTOX 72 U/BOTOX 72 U and Total). The only

exception is BOTOX cycle 3, where participants will be summarized by BOTOX 72 U/BOTOX 72 U.

Overall summary of AEs will be provided on a per-participant basis for categories of TEAEs, treatment-related TEAEs, deaths, serious adverse events (SAEs), AEs leading to discontinuation, and possible distant spread of toxin (PDSOT).

The number and percentage of participants reporting TEAEs in each treatment group will be tabulated by system organ class (SOC) and preferred term, and further categorized by severity and causal relationship to the study treatment separately. If more than 1 AE is coded to the same preferred term for the same participant, the participant will be counted only once for that preferred term using the greatest severity and strictest causality for the summarization by severity and causal relationship.

The incidence of TEAEs will be summarized by preferred term and treatment.

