#### 17.2 TREATMENT CYCLES

A treatment cycle is considered to start on the day of treatment with study medication and end on the day prior to the next study treatment or on the study exit day if there are no subsequent treatments.

[figure not shown]

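### Cycle 1 adverse-event tables run past Day 180 until response-dependent retreatment or exit, so the only randomised safety comparison can rest on unequal follow-up

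*SAP*

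**What the plan says.** Three rules set the cycle 1 safety window.

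- SAP 10.0, for participants who continue into Period 2: "safety data beyond Day 180 but prior to retreatment (if any) will be ascribed to the double-blind treatment received in treatment cycle 1".
- SAP 17.2: a cycle starts on the day of treatment and will "end on the day prior to the next study treatment or on the study exit day if there are no subsequent treatments". There is no cap at Day 180.
- Protocol 6.6.1, first retreatment criterion: "Participant has presence of MMP of at least marked (Grade 4) on each side, as measured by the investigator using the MMPS". Treatment 2 is possible from the Day 180 visit to the Day 420 visit, and a participant who qualifies may decline (Protocol 4.1). Protocol 4.1 adds that "retreatment timepoints are not expected to be synchronized among the participants in the study".

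The summaries are simple. SAP 10.2: "The number and percentage of participants reporting TEAEs in each treatment group will be tabulated by system organ class (SOC) and preferred term". SAP 10.1: "The number of treatments received will be summarized by treatment group for the Safety Population". The visible text gives no follow-up duration, person-time rate or Day 180 cut-off. SAP 7.0 reports disposition by cycle, Protocol 9.4.2.1 promises listings, and SAP 4.0 refers table specifications to a separate document that is not available here.

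On labelling, SAP 10.2 states: "TEAEs will be summarized for each treatment group by treatment cycle 1 in the double-blind period, open-label period". SAP 4.0 states: "Period 1 (Days 1 through 180) will be a double-blind, randomized, placebo-controlled, single-treatment design".

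**The concern.** Comparing safety with placebo is a primary objective (SAP 5.1). The other adverse-event tables cover open-label treatment or BOTOX exposure, so cycle 1 is the only place where randomised arms can be compared.

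Under the written rule, the length of cycle 1 depends on treatment response. A participant back at Grade 4 on both sides at Day 180 who accepts retreatment contributes about 180 days. One who stays below Grade 4 to the end contributes about 540. A crude percentage rises with time at risk, so two arms with the same event rate can show different percentages.

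Longer follow-up on BOTOX is the likely direction. Protocol 4.3 reports that Phase 2 efficacy lasted at least 6 months, with median time to loss of MMPS response of up to 9 months in some participants. That would overstate background events on BOTOX. If many placebo participants stay below Grade 4, the sign reverses.

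Two smaller points of wording sit in SAP 10.2:

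- The label ties cycle 1 to the double-blind period, which ends at Day 180, while SAP 10.0 and 17.2 let cycle 1 run on.
- The cycle 1 TEAE sentence covers new onset and becoming serious but omits an increase in severity. The general SAP definition and Protocol 9.4.2.1 both include it. The gap mainly affects events that began between consent and Day 1 and later worsened without becoming serious.

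**Working it through.** **The plan's own figures.** 306/(1 - 0.15) = 360, and a 3:1 split gives 270 and 90, as stated. The visible text gives no adverse-event incidence or cycle length for this trial, so there is no further figure to reproduce.

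**Range of cycle 1.** The shortest is about 180 days and the longest is 540 days, a ratio of 540/180 = 3.

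**Effect of time alone.** Assume a constant background hazard, equal in both arms, with risk p by Day 180. The risk by day T is 1 - (1 - p)^(T/180). At p = 0.30 this is 30.0% at 180 days, 41.4% at 270, 51.0% at 360 and 65.7% at 540.

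**Example that can be checked by hand** (assumed mixes, no dropout):

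- Placebo: 80% end cycle 1 at Day 180, 10% at 270 and 10% at 540. Mean 225 days. Risk 0.8 × 0.300 + 0.1 × 0.414 + 0.1 × 0.657 = 34.7%.
- BOTOX: 50% at 180, 30% at 270, 10% at 360 and 10% at 540. Mean 261 days. Risk 0.5 × 0.300 + 0.3 × 0.414 + 0.1 × 0.510 + 0.1 × 0.657 = 39.1%.
- Difference +4.4 points with no true difference.

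**Fuller model.** Only the 15% dropout is from the documents (Protocol 1.1). It is applied equally to both arms as an exponential rate of -ln(0.85)/540 per day. The remaining inputs are assumptions:

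- Base case: 50% of BOTOX and 10% of placebo are below Grade 4 at Day 180.
- BOTOX non-qualifiers requalify after an exponential time with median 30, 60 or 90 days, rounded up to the next 30-day visit.
- Placebo non-qualifiers either wane in the same way or stay below Grade 4.
- 95% of those who qualify accept at each visit.
- Anyone not retreated by Day 420 runs to Day 540.

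Base case at p = 0.30 (values good to about 0.1 point):

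| BOTOX median to requalify | Mean days, BOTOX | Mean days, placebo (wane / stay) | Spurious difference, points (wane / stay) |
|---|---|---|---|
| 30 days | 205 | 182 / 209 | +2.8 / +0.4 |
| 60 days | 224 | 186 / 209 | +4.5 / +2.4 |
| 90 days | 241 | 190 / 209 | +5.8 / +4.1 |

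At p = 0.20 the base-case range is +2.1 to +4.5 (wane) or +0.1 to +3.1 (stay). At p = 0.40 it is +3.4 to +6.6 or +0.8 to +4.9.

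Other shares below Grade 4 at Day 180, at p = 0.30:

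| BOTOX / placebo share | Wane | Stay |
|---|---|---|
| 70% / 10% | +4.3 to +8.8 | +1.8 to +7.0 |
| 30% / 10% | +1.4 to +2.9 | -1.1 to +1.2 |
| 30% / 30% | 0 | -7.5 to -5.3 |

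Across all these scenarios the ratio of mean follow-up, BOTOX to placebo, is 0.71 to 1.41.

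**Scale.** The standard error of a difference at 30% is sqrt(0.30 × 0.70 × (1/270 + 1/90)) = 5.6 points. Five of the six base-case values are below it.

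**Check on the remedy.** Cutting T at Day 180 gives a difference of 0 in every scenario, because both arms then have the same window and the same assumed dropout.

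**The case against.** **The label may already mean Days 1 to 180.** On that reading SAP 10.0 only says which treatment later events belong to. But SAP 10.0 states a rule for all safety data after Day 180, and SAP 17.2 agrees with it. A loose label does not override two explicit rules.

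**The table specifications may hold a cut-off or a follow-up row.** That is possible and cannot be checked. The finding is limited to the visible text, but the window for a primary objective should be stated in the SAP.

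**The rule has a purpose.** It gives a place to late events in participants who are never retreated. This is a good reason to keep the full cycle 1 table, though not to use it as the randomised comparison.

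**The size is uncertain and often small.** This stands. At preferred-term level, with the 50%/10% shares and a 60-day median, an assumed 4% risk by Day 180 gives +0.3 to +0.8 points against a standard error of 2.4. An assumed 8% gives +0.7 to +1.6 against 3.3. If 40% or 60% of the 180-day hazard falls in the first 30 days, the +4.5 figure drops to +3.4 or +2.4. On the other side, this is a systematic error that does not average out, and the standard error does not reveal it.

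**The consequences are limited.** This also stands. Adverse reactions generally appear within days to weeks (Protocol 2.3), SAP 10.2 also tabulates events by causal relationship, and no adverse-event test is stated. In the likely direction the error counts against BOTOX and would not hide harm.

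**Conclusion.** The concern holds and should be fixed. As written, the randomised adverse-event comparison uses an observation window that depends on response and can differ threefold between participants, with no visible adjustment. This follows from the text alone, and confidence in it is high.

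Confidence in size and sign is low. The documents give neither the share of each arm below Grade 4 at Day 180 nor the event rates. At an assumed 30% risk by Day 180 the artefact spans -7.5 to +8.8 points, including 0. These figures rest on a constant and equal hazard, equal dropout in both arms and the stated response patterns, and they describe background events only. No efficacy result, alpha or power is affected. The label and the TEAE wording are editorial.

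**What to change.** In SAP 10.0 and 10.2:

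1. Base the BOTOX-versus-placebo adverse-event comparison on a table from Day 1 to the Day 180 visit, before any retreatment, or to exit if earlier.
2. Keep the full cycle 1 table as supplementary, with follow-up duration and exposure-adjusted rates by arm.
3. Reword the cycle 1 label so that it agrees with SAP 10.0 and 17.2.
4. Add increase in severity to the cycle 1 TEAE definition.

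The cost is SAP wording, one extra table, a follow-up row and a little programming. No data are lost, and no treatment or retreatment rule changes.
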